12.8.1.1 TEAEs

A breakdown of the number and percentage of patients reporting each AE categorized by SOC and PT will be presented. Note that patients are only counted once within each SOC or PT if an AE was reported more than once.

The following summaries of TEAEs will be presented by SOC and PT, where related is defined as a 'suspected' relationship to study treatment, combination treatment related is defined as being related to either SOT101 or pembrolizumab (or both), and discontinuation of combination treatment means discontinuation of either SOT101 or pembrolizumab (or both):

- Patients reporting at least one TEAE
- TEAEs occurring in $\geq 5\%$ of patients
- Patients reporting at least one SOT101-related TEAE
- Patients reporting at least one Combination treatment related TEAE
- Patients reporting at least one CTCAE Grade 3 or greater TEAE
- Patients reporting at least one CTCAE Grade 3 or greater SOT101-related TEAE
- Patients reporting at least one CTCAE Grade 3 or greater combination treatment-related TEAE
- Patients with at least one AESI
- Patients with TEAEs leading to dose reduction or temporary discontinuation of SOT101
- Patients with TEAEs leading to dose reduction of SOT101
- Patients with TEAEs leading to temporary discontinuation of SOT101
- Patients with TEAEs leading to delay of administration of pembrolizumab,
- Patients with TEAEs leading to permanent discontinuation of SOT101
- Patients with TEAEs leading to permanent discontinuation of pembrolizumab
- Patients with TEAEs leading to permanent discontinuation of combination therapy
- Patients with treatment-related TEAEs leading to permanent discontinuation of SOT101
- Patients with non-serious TEAEs reported in $\geq 5\%$ of patients

The following summaries will be presented by PT in descending order of frequency:

- Patients reporting at least one TEAE
- Patients reporting at least one SOT101-related TEAE
- Patients reporting at least one combination treatment-related TEAE
- TEAEs occurring in $\geq 5\%$ of patients
- Patients reporting at least one CTCAE grade 3 or greater TEAE for PTs occurring in at least 5% of patients,

The following summaries will be presented by SOC, PT, and maximum CTCAE grade:

- Patients reporting at least one TEAE
- Patients reporting at least one SOT101-related TEAE.

All AEs (including non-treatment-emergent events) recorded on the CRFs will be listed using the ASaT population. The following listings will be produced separately:

- All AEs
- AEs leading to death
- Treatment-emergent SAEs
- TEAEs leading to permanent discontinuation of SOT101
- TEAEs leading to temporary discontinuation of SOT101
- TEAEs leading to permanent discontinuation of pembrolizumab
- TEAEs leading to temporary discontinuation of pembrolizumab
- TEAEs leading to dose reduction of SOT101
- TEAEs of special interest

The following summaries will be presented by PT in descending order of frequency, and maximum CTCAE grade broken down into the categories Any Grade, Grade 1/2, Grade 3, Grade 4 and Grade 5:

- Any TEAE
- Any SOT101-related TEAE.
- Any Combination-treatment related TEAE
- TEAEs reported in ≥10% of patients

Additionally a bar chart showing TEAEs occurring in ≥10% of subjects will be presented, sorted by most prevalent TEAE and with the bar broken down to represent CTCAE grades 1 or 2, 3, or 4.

12.8.1.2 SAEs and Deaths

The following summaries of SAEs, including AEs that lead to death, will be presented by SOC and PT:

- Patients with at least one SAE
- Patients with at least one SOT101-related SAE
- Patients with at least one combination treatment-related SAE
- Patients with an AE leading to death
- Patients with a treatment-related TEAE leading to death (related to SOT101)
- Patients with a treatment-related TEAE leading to death (related to combination treatment)

The following summaries will be presented by PT in descending order of frequency:

- Patients reporting at least one SAE
- Patients reporting at least one treatment-related SAE (related to SOT101) Patients reporting at least one combination treatment-related SAE (related to either SOT101 or Pembrolizumab)

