#### **8.3.2 Time period and frequency for collecting AE, SAE, and other reportable safety event information**

Every effort should be taken to collect all AEs, AESIs, and SAEs from the date of the patient’s signing the ICF until 90 days after the final administration of nanrilkefusp alfa and/or pembrolizumab (whichever is later) or until the start of a new anti-cancer therapy, whichever is earlier.

---

Additionally, any SAE brought to the attention of an investigator at any time outside of the time period specified above must be reported immediately to the sponsor or designee if the event is considered as having a suspected causal relationship to nanrilkefusp alfa and/or pembrolizumab per the investigator's judgment.

Pregnancies of the patient or patient's female partner must be reported from the date of the patient's signing the ICF up to 120 days following the last dose of pembrolizumab or 30 days after the last dose of nanrilkefusp alfa, whichever is later.

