### **9.3.3 Secondary endpoints analysis**

#### **9.3.3.1 Safety endpoints**

- TEAEs

A TEAE is defined as an AE that started or worsened at or after the start of study treatment.

TEAEs will be summarized with counts and percentages. These will be provided for the incidence of, but not limited to: any TEAE, any serious TEAE, any grade 3-5 TEAE, any drug-related TEAE, any serious and drug-related TEAE, any grade 3-5 and drug-related TEAE, temporarily discontinued due to a TEAE, permanently discontinued due to a TEAE, death. TEAE incidence frequencies by system organ class (SOC) and preferred term (PT) will also be provided.

- AESIs

AESIs will be summarized with counts and percentages by SOC and PT.

- Safety laboratory findings, vital signs, and ECG

Safety laboratory findings, vital signs measurements, and ECG data will be summarized accordingly (if categorical or continuous data). Laboratory results will be summarized using SI units as appropriate.

Further details on analyses to be performed by indication and overall will be specified in the final SAP.

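### The SAP's any-SAE tables carry no treatment-emergent limit, although the protocol names serious TEAEs and the SAP's own SAE listing is limited to treatment-emergent events

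*SAP*

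**What the plan says.** **Protocol.** Section 9.3.3.1 (Safety endpoints) lists the incidences to be summarized, among them "any serious TEAE, any grade 3-5 TEAE" and, further on, TEAEs that are both serious and drug-related. The list is open-ended, and it also names death without a treatment-emergent qualifier. Section 8.3.2 sets the collection window: "Every effort should be taken to collect all AEs, AESIs, and SAEs from the date of the" patient's consent signature, up to 90 days after the last dose or the start of a new anti-cancer therapy if that is earlier. Section 4.1.1 allows up to 28 days of screening.

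**SAP.** Section 12.8.1.1 covers TEAEs. It has a table of non-serious TEAEs but none of serious TEAEs. Its listings include "Treatment-emergent SAEs", and it also says "All AEs (including non-treatment-emergent events) recorded on the CRFs will be listed using the ASaT population". Section 12.8.1.2 opens with its own lead-in, "The following summaries of SAEs, including AEs that lead to death, will be presented by SOC and PT", and its first row is "Patients with at least one SAE". The any-SAE summary appears again there by preferred term. The same list does use the treatment-emergent term for the drug-related death rows, for example "Patients with a treatment-related TEAE leading to death (related to SOT101". Section 12.8 puts these tables on the ASaT population, that is, treated patients. Section 6.1 (Changes from Protocol) does not mention the move from serious TEAE to SAE.

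**The concern.** The protocol and the SAP's own listing use one set of events for serious cases, and the SAP's tables, as worded, use a wider one. This has three consequences.

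- A summary that the protocol says will be provided is not specified as a table anywhere in the SAP, and the replacement is not declared.
- The any-SAE count can exceed the number of patients in the SAE listing that should support it.
- The serious and non-serious tables rest on different events, because the non-serious table is limited to TEAEs.

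This is a single-arm study, so a reader will take the any-SAE row as the serious-event rate under the combination. No control column shows how many such events belong to the disease or to screening.

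**Working it through.** The plan states no SAE rate, so there is no figure to reproduce. The check compares the definitions, then sizes one misplaced patient.

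**1. Which events differ.** SAP 10.15.1 defines a TEAE by onset or worsening once treatment has begun, and sets no closing date. SAEs that start after dosing are therefore treatment-emergent however late they occur. The two definitions part only for SAEs that began before the first dose and did not worsen.

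**2. Where each type of SAE lands, reading the SAP literally.**

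| SAE | Protocol serious-TEAE summary | SAP any-SAE tables | SAP treatment-emergent SAE listing | SAP all-AE listing |
|---|---|---|---|---|
| Treated patient, onset after first dose | yes | yes | yes | yes |
| Treated patient, pre-dose onset, worsened after dosing | yes | yes | yes | yes |
| Treated patient, pre-dose onset, not worsened | no | **yes** | no | yes |
| Screen failure, never treated | no | no | no | no |

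Only the third line is inconsistent.

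**3. Which rows are exposed.** The any-SAE row is exposed, by SOC and PT and again by PT. The related-SAE rows need a suspected relationship to study drug, which is hardly plausible before any drug was given, so they are practically unaffected.

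**4. Size per patient.** Each treated patient whose only SAE was pre-dose adds 1/n to the any-SAE rate:

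- n = 50 (smallest planned cohort, protocol 9.5 and SAP 8.1): 1/50 = 2.0 points.
- n = 57 (largest planned cohort): 1/57 = 1.8 points.
- n = 320 (planned total; SAP 12.8 also summarizes safety overall): 1/320 = 0.3 points.

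SAP 6.1 records that recruitment stopped after the August 2023 futility analysis, and final cohort sizes are not given. If a cohort ended at its futility-look size, one patient would be 1/21 = 4.8 points or 1/12 = 8.3 points.

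**5. Illustration on assumed rates.** Let p be the share of treated patients with a pre-dose SAE that did not worsen, and q the share of those who also have a treatment-emergent SAE. Only patients without a treatment-emergent SAE raise the rate, so the increase is p × (1 − q). Neither p nor q is in the documents. Assuming p = 1% to 5% and q = 30%:

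- lower: 0.01 × 0.70 = 0.7 points, about 2 of 320 patients (320 × 0.007 = 2.2);
- upper: 0.05 × 0.70 = 3.5 points, about 11 of 320 patients (320 × 0.035 = 11.2).

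**The case against.** **The qualifier may simply have been left out.** No sentence in the SAP says that the tables count from consent; that follows from a missing word and the collection window. The SAP is loose in the same way elsewhere: its AESI table has no qualifier of its own, yet stands under a TEAE lead-in, and the matching listing is of TEAEs of special interest. The non-serious TEAE table suggests that 12.8.1.2 was meant as its serious counterpart. This stands as a statement of probable intent, but it does not settle the wording. Section 12.8.1.2 has a separate lead-in that speaks of SAEs, and the same list uses the treatment-emergent term elsewhere. A programmer following the text would apply no filter.

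**The protocol's list is open-ended.** An added all-SAE table would not in itself be a departure. This is right, and a reader should not infer that section 9.3.3.1 defines the safety endpoint as serious TEAEs: it lists summaries, and the endpoint is broader. But an open-ended list permits additions, not the omission of items it names.

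**The death row.** A reader might infer that it has the same fault. The documents do not support that. The protocol names death without a qualifier, and the SAP's listing of AEs leading to death is worded like the table row. A pre-dose event that later kills a treated patient has worsened, so it is a TEAE anyway. Restricting the row would create a mismatch with its listing.

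**Few events are at issue.** Screen failures are outside the ASaT population. Protocol 8.3.1.4 does not treat hospitalization for study procedures without deterioration as serious, so an uncomplicated screening biopsy would not count. A serious screening event may also make a patient ineligible. All of this stands and points to a small number.

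**Nothing is hidden.** Pre-dose SAEs stay in the all-AE listing, any error overstates harm, and neither the primary endpoint nor the futility rule is touched. This also stands.

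**Conclusion.** The inconsistency is real, and its scope is narrow. Protocol 9.3.3.1 calls for serious-TEAE summaries, the SAP specifies no such table, its any-SAE tables are wider as worded, its SAE listing is not, and SAP 6.1 is silent. The conclusion rests on reading SAP 12.8.1.2 literally and on SAEs being collected from consent.

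The effect on the reported rate is probably small: 2.0 points per affected patient in a cohort of 50 and about 0.3 points in the planned 320. A reader might infer that the any-SAE rate will be inflated by several points. The documents give no screening SAE rate, so they do not support that; the 0.7 to 3.5 points above depend wholly on the assumed p and q. The case for correcting the SAP is that a summary named in the protocol is missing and that table and listing would not reconcile, not a known distortion.

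**What to change.** **Preferred.** In SAP 12.8.1.2, restrict the SAE tables (by SOC and PT, and by PT) to treatment-emergent SAEs. This brings them into line with protocol 9.3.3.1 and with the SAP's SAE listing. Keep pre-treatment SAEs in the all-AE listing, and leave the row for AEs leading to death as it is.

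**Alternative.** Keep the all-SAE tables, add the serious-TEAE table, widen the SAE listing to match or add an all-SAE listing beside it, and declare the change in SAP 6.1.

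The preferred change costs a few words and a filter in the table programs. The alternative costs one or two extra outputs and an entry in 6.1. Neither needs new data.

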12.8.2 Laboratory Data

12.8.2.1 Laboratory Parameters

Clinical laboratory parameters to be collected on-study are referenced in the protocol section 8.2.5**Error! Reference source not found.** Standard International units documented in the local laboratory conventions will be used for all laboratory parameters.

Quantitative data will be summarized using descriptive statistics of actual values and CFB for each scheduled visit over study. Only selected parameters will be summarized and plotted: Hemoglobin, Platelets, Neutrophils, Lymphocytes for hematology; ALT, Albumin, Alkaline phosphatase, AST, Total Bilirubin, Creatinine, Creatinine clearance, Lactate dehydrogenase, and C-reactive protein for chemistry. D-Dimer for Coagulation.

All laboratory data will be summarized in International System (SI) units. Conversion for local laboratories will be performed in the RAVE Lab Tool according to the study Local Lab Conventions. In general, laboratory data will be presented by visit. Values at unscheduled visits will be included in the summary of maximum for all cycles and minimum for all cycles, which will present the largest and smallest values observed for each patient on-treatment for each test.

The actual values for each scheduled visit up to and including cycle 10 for selected laboratory parameters will be plotted for each indication. Box plots will be produced showing the summary data per indication per scheduled assessment, including an overlaid mean profile line and approximate LLN and ULN lines indicated (see Appendix I).

Laboratory values evaluated as abnormal will be presented in separate listing.

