### 8.3.8 Reporting by the investigational site

#### 8.3.8.1 Adverse events

Any AE, whether or not considered to be causally related to the trial medication and regardless of its seriousness, must be reported (described and recorded) in the AE section of the patient's eCRF on an ongoing basis. Each AE will be evaluated by the investigator to determine its term and grade according to the CTCAE, version 5.0. In case a suitable CTCAE term is not available, an appropriate medical verbatim term may be used instead.

Only clinically relevant abnormal laboratory values, vital signs, or examination abnormalities need to be documented as AEs. Whenever possible, a diagnosis rather than symptoms should be provided on the AE eCRF page (e.g., anemia instead of low hemoglobin).

Clinically relevant here means: induce clinical signs or symptoms, require therapy (e.g., hematologic abnormality requiring treatment), require a change in trial medication(s), or require a change in the clinical trial schedule or per investigator's discretion.

Physical examination findings will be compared with the baseline status and any significant change, as assessed by the investigator, must be documented as an AE.

A surgical procedure is not an AE but a therapeutic measure for a condition that necessitates surgery. Therefore, the condition for which the surgery is required has to be reported as an AE.

Any pre-planned surgery (i.e., planned before signature of the ICF) or other intervention permitted by this study Protocol and the condition leading to that measure are not AEs. In such cases, the underlying condition needs to be documented in the patient's medical history on the eCRF.

Death itself is not an AE term but the outcome of an event, which needs to be described using medical terminology. Information about death will be captured on the respective eCRF page along with relevant details (date of death, immediate and underlying causes of death).

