7.2 Secondary Objectives

- To assess the safety and tolerability of SOT101 in combination with pembrolizumab according to Common Terminology Criteria for Adverse Events (CTCAE) version 5.0
- To further evaluate the antitumor efficacy of SOT101 in combination with pembrolizumab
- (Population) pharmacokinetics (PK) of SOT101 in combination with pembrolizumab
- To determine the immunogenicity of SOT101 in combination with pembrolizumab

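### SAP 12.8.2 plans no CTCAE-graded or baseline-to-worst shift summary of laboratory values, so grade 3-4 values not recorded as adverse events are not counted by grade

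*SAP*

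**What the plan says.** SAP 7.2 sets the safety objective "according to Common Terminology Criteria for Adverse Events (CTCAE) version 5.0". The endpoint table in SAP 7.4 names safety laboratory findings beside treatment-emergent AEs, AEs of special interest, vital signs and ECG.

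For laboratory data, SAP 12.8.2.1 states: "Quantitative data will be summarized using descriptive statistics of actual values and CFB for each scheduled visit over study". It then restricts the tests: "Only selected parameters will be summarized and plotted". The selected tests are:

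- Hematology: hemoglobin, platelets, neutrophils and lymphocytes
- Chemistry: "ALT, Albumin, Alkaline phosphatase, AST, Total Bilirubin, Creatinine, Creatinine clearance, Lactate dehydrogenase, and C-reactive protein for chemistry"
- Coagulation: "D-Dimer for Coagulation"

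It adds a summary over all cycles that takes in unscheduled visits, "which will present the largest and smallest values observed for each patient on-treatment for each test". There are also box plots up to cycle 10 and a separate listing of abnormal values. SAP 12.8.2.2 adds counts and percentages of patients meeting Hy's law, an eDISH figure and a listing of patients at risk. SAP 12.8.2.3 adds four thyroid tests.

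CTCAE grading appears in SAP 12.8 and 12.8.1 and is applied to AEs. For what becomes an AE, Protocol 8.3.8.1 states: "Only clinically relevant abnormal laboratory values, vital signs, or examination abnormalities need to be documented as AEs". It explains relevance as symptoms, a need for therapy, a change in trial medication or schedule, or the investigator's discretion. It sets no grade threshold.

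**The concern.** An endpoint called safety laboratory findings, under an objective framed by CTCAE, would normally be read as yielding the number of patients who reached each grade. The laboratory section does not produce that number. The AE tables produce it only for abnormalities that pass a judgement of clinical relevance, and that judgement may differ between investigators and sites.

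This matters for this drug. Protocol 2.3 reports that in the earlier study decreased lymphocyte count was a treatment-emergent AE in 66.7% of patients on monotherapy and 47.6% on the combination. Decreased lymphocytes and anemia were among the most common events above grade 2. Here, whether an asymptomatic fall in lymphocytes is counted depends on each investigator. A table graded from the laboratory values themselves would not.

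**Working it through.** The documents give no figure to reproduce on this point. The check is a count of tests and a comparison of sections.

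**1. Tests summarized.** The lists in SAP 12.8.2.1 give 4 hematology + 9 chemistry + 1 coagulation = 14. With the 4 thyroid tests of SAP 12.8.2.3, 14 + 4 = 18.

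**2. Tests collected.** Protocol 8.2.5.3 lists 24 chemistry tests, counting direct and total bilirubin separately and urea or blood urea nitrogen as one. Nine are selected, so 24 - 9 = 15 have no planned summary; these include the electrolytes, glucose, amylase and lipase. Protocol 8.2.5.1 lists 5 coagulation tests. One is selected, so 5 - 1 = 4 have no planned summary, including INR.

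**3. Graded laboratory outputs planned.** Reading SAP 12.8.2.1 to 12.8.2.3 for any grade, worst-grade table or shift table gives 0. The only threshold count is Hy's law. For comparison, SAP 12.8.5.2 does plan threshold categories for QTcF, which belongs to the same endpoint.

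**4. Can the planned outputs stand in for a graded count?**

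- *Maxima and minima.* These summarize a distribution and do not give the number of patients at each grade. Footnotes a to c of Protocol Table 6.3 define the liver grades as multiples of ULN, or of baseline when baseline is abnormal. SAP 12.8.2.1 pools local-laboratory values after conversion to SI units, and SAP Appendix 1 draws one approximate upper limit of 105 U/L for ALT and AST. A pooled maximum in U/L therefore does not translate into a grade.
- *Baseline.* Inclusion criterion 11 admits ALT/AST up to 5 x ULN with liver metastasis. A patient who enters at 5 x ULN and stays there has the same maximum, in multiples of ULN, as one who rises to 5 x ULN from normal. Only the second has worsened, and without a shift the two look alike in the maximum.
- *Period.* SAP 10.6 ends the on-treatment period no later than the day before the end-of-treatment visit. Protocol 1.3.3 schedules hematology, biochemistry and coagulation at that visit. Those values fall outside the on-treatment extremes.
- *Hy's law.* It requires a concurrent bilirubin rise, so an isolated enzyme rise is not counted there.
- *Listings.* They show individual values and give no incidence.

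**5. What the AE tables do cover.** An abnormality that is symptomatic, treated, or leads to a change in study medication or schedule is an AE under Protocol 8.3.8.1. It then enters the grade 3 or greater and maximum-grade tables of SAP 12.8.1.1. The uncovered remainder is grade 3-4 values meeting none of those conditions and not reported at the investigator's discretion.

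**The case against.** The strongest reply is that no commitment is broken. Protocol 8.3.7.2 and 8.3.8.1 attach CTCAE grading to AEs, and Protocol 9.3.3.1 promises only that laboratory findings be summarized as suits categorical or continuous data. The SAP does that. This stands: the point is a better summary, and the plan does not contradict itself here.

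A reader might go further and infer that grade 3-4 laboratory toxicity in general goes uncounted. The documents do not support that. Protocol Table 6.2 calls for withholding nanrilkefusp alfa for drug-related hepatic values of grade 2 or higher. Such a value changes trial medication, so it is an AE and is counted by grade. The earlier study also shows laboratory events reaching the AE tables above grade 2.

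A reader might also infer that averaging by visit hides isolated extremes. That fails too. The descriptive statistics in SAP 12.0 include minimum, quartiles and maximum, the per-patient extremes include unscheduled visits, and cycle 1 hematology is scheduled on days 1, 2, 6, 8, 9 and 13. An extreme value would be visible. The number of patients at each grade would not be.

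Finally, INR enters one of the protocol's liver criteria for AEs of special interest, which might suggest that those events are lost without an INR summary. They are not: the SAP identifies them from the AE page, and the protocol has sites report them within 24 hours.

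**Conclusion.** The point holds in a limited form and is worth acting on. The SAP plans no graded or shift summary of laboratory values. Grade 3-4 values not judged clinically relevant, such as asymptomatic lymphopenia or raised lipase, appear in listings or, for the selected tests, as ungraded extremes, and are not counted by grade. Most collected chemistry and coagulation tests (15 of 24 and 4 of 5) have no planned summary at all.

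The size in patients cannot be stated. It depends on how often investigators leave high-grade values unreported, and the documents give no such figure. Cohort sizes are also below plan, since SAP 6.1 records that recruitment stopped after the August 2023 futility analysis.

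The conclusion rests on two readings: that the restriction to selected tests also governs the maximum and minimum summary, and that tests such as lipase carry a CTCAE v5.0 grade. The documents do not reproduce the CTCAE table. The primary efficacy analysis is unaffected.

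**What to change.** In SAP 12.8.2.1, add a table of worst post-baseline CTCAE v5.0 grade and shift from baseline grade for every collected test that has a grade. Use scheduled, unscheduled and end-of-treatment values, apply each local laboratory's normal range (and baseline where the grade depends on it), and present it for the ASaT population by indication and overall. State the post-baseline window explicitly, since the on-treatment period in SAP 10.6 leaves out the end-of-treatment visit.

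The cost is modest extra programming to derive grades from local ranges across several tests. No new data or procedures are needed, and the Hy's law outputs already require values relative to ULN. SAP 6.0 has the plan finalized before database lock, and the table should be specified by then.
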